**6.2.4. Visit 31/Day 1093/Week 156 through Visit 43/Day 1765/Week 252 (+/-3 Days)**

The study treatment duration will be up to 5 years. Visits 31 through 43 will occur approximately every 8 weeks until the end of treatment.

The following information will be collected:

- Concomitant medications/procedures: visit 31, 33, 35, 37, 39, 41, and 43.
- AEs
- Informed consent for the optional sub-study using the new dupilumab drug product: visit 41 or 43. See Section 6.2.6 for further information about procedures and assessments to be performed during the sub-study.

The following procedures and assessments will be conducted:

- IGA/EASI: visit 31, 37
- Weight: visit 31, 33, 35, 37, 39, 41, and 43
- Vital signs (heart rate, blood pressure, body temperature, and respiration rate): visit 31, 33, 35, 37, 39, 41, and 43
- Ophthalmology exam (select sites and patients): visit 31, 33, 35, 37, 39, 41, and 43)
- Patient assessment of pruritus intensity via IVRS/IWRS (weekly)
- Laboratory samples:
  - Hematology w/differential: visit 37
  - Serum chemistry: visit 37
  - Urine pregnancy test – for women of childbearing potential. Starting at visit 31 monthly until visit 43, urine pregnancy test must be negative before dosing.
  - ADA sample: visit 33 and 39
- Confirm that the patient completed/reported the dosing diary for each dose of study drug that was administered outside of the clinic
- Study drug dispensation/ accountability
- Administer study drug (weekly throughout the study)

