2.2. Sample Size and Power Considerations

Based on the numbers of patients enrolled or screened in the antecedent dupilumab studies, it is anticipated that approximately 2500 patients will be enrolled in this global study. By then end of May2017, the study enrollment is completed. There are 2678 patients enrolled.

No formal sample size or power calculations were performed for this study.

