Under protocol amendment 6, the planned study duration was up to three years or until dupilumab became commercially available in the geographic region of the patient. Protocol amendment 7 was adopted in order to permit those patients in France, Germany, Poland and Japan who had already completed three years of treatment to either continue or re-start treatment through 31 December 2017. Patients who were in the 16-week safety follow-up period were permitted to resume treatment. Patients who had an End of Study visit were permitted to re-enter the study after being re-consented. Patients who had completed 3 years of treatment resumed treatment in a newly created series of visits called the “treatment extension” period. All patients were scheduled to have an End of Treatment visit on or around 31 December 2017.

Protocol amendment 8 extended the treatment period for up to 5 years for patients in Poland and Finland and to September 2018 in France. Again, patients who had previously had an End of Treatment visit under Amendment 7 and were in the 12-week safety follow-up period were permitted to resume treatment. Patients who had an End of Study visit were permitted to re-enter the study after being re-consented. This is illustrated in Figure 1.

As a consequence of these two amendments, certain patients from these countries experienced gaps in treatment. One gap occurred between the Amendment 6 end of treatment (EoT) date and resumption of treatment under Amendment 7 for approximately 113 patients with a median duration of gap around 17 weeks and maximum duration of around 33 weeks. In addition, there are approximately 272 patients from Poland, Finland and France who experienced a second treatment gap from the EoT date under Amendment 7 and resumption of treatment under Amendment 8 with a median duration of gap around 10 weeks and maximum duration of around 21 weeks.

Figure 1: Overall Study Flow Diagram Showing the Treatment Gap due to Protocol Amendment 7 and 8

[figure not shown]
[figure not shown]

Figure 2: Study Flow Diagram for Protocol Amendment 7 (Global)

^a Patients who fail screening or who fail to complete the baseline visit within 28 days of screening may be rescreened upon approval by the medical monitor.

[figure not shown]

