^b A loading dose of 600 mg SC (two 300 mg doses administered on the same day) dupilumab will be administered on day 1 unless the patient has received a dose of dupilumab in the 4 weeks prior to baseline. If the patient has received a dose of dupilumab in the past 4 weeks, then they will receive a single 300 mg dose at baseline. The first dose should be at least 1 week after the last dose in the previous study, and then 300 mg dupilumab qw starting on day 8.

^c Patients will be monitored at the study site for a minimum of 30 minutes at the baseline visit.

^d Visits 10, 12, 14, and 16 have been removed per amendment 6. This yields a schedule in which visits are 8 weeks apart from week 16 through week 48. The week 48 visit is followed by a visit at 52 weeks, then visits occur every 8 weeks thereafter up to and including the End of Treatment visit (week 148).

^e Visits 3, 4, 5, and 7 were removed per amendment 6.

^f Patients who have completed their End of Study (EOS) visit and are resuming treatment per Amendment 7 may re-enter the trial at visit 31 after the trial re-entry visit. Patients who have completed their End of Treatment (EOT) visit may resume treatment at visit 31.

^g All patients will be scheduled for an EOT visit on or about 31 December 2017.

Figure 5: Study Flow Diagram for Protocol Amendment 8 (Poland, Finland)

Screening		Treatment Period ^{b, c}									
	Baseline										
V1 D-28 to D- 1 ^a	V2 D1	V3 ^e W1	V4 ^e W2	V5 ^e W3	V6 W4	V7 ^e W8	V8 W12	V9-V30 ^d W16- W148 (every 8 weeks)	V31 ^{f, g} -V43 (every 8 weeks)	V44/EOT ^g	EOS 12 weeks after last dose

^a Patients who fail screening or who fail to complete the baseline visit within 28 days of screening may be rescreened upon approval by the medical monitor.

^b A loading dose of 600 mg SC (two 300 mg doses administered on the same day) dupilumab will be administered on day 1 unless the patient has received a dose of dupilumab in the 4 weeks prior to baseline. If the patient has received a dose of dupilumab in the past 4 weeks, then they will receive a single 300 mg dose at baseline. The first dose should be at least 1 week after the last dose in the previous study, and then 300 mg dupilumab qw starting on day 8.

^c Patients will be monitored at the study site for a minimum of 30 minutes at the baseline visit.

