5.7. Analyses of Efficacy Variables

The efficacy variables will be summarized for all patients in SAF. The continuous efficacy variables will be summarized using number of patients, means, SD, minimums, medians, Q1, Q3 and maximums. Categorical efficacy variables will be summarized using patient counts and proportion. No formal statistical hypothesis testing will be performed. The graph of mean value for continuous variable or proportion for categorical variable by visit will be provided.

All observed values, regardless of whether rescue treatment is used or data is collected after withdrawal from study treatment will be used for analysis. No missing values will be imputed.

For the categorical efficacy variables, the proportion of patients with each response at each visit will be calculated using the number of patients with a non-missing value at the visit as the denominator.

As described in Section 5.6, there are up to two potential “treatment gaps” due to patient re-entry to the study for protocol amendments 7 and 8 for patients from Germany, France, Poland and Japan. The primary focus of the efficacy data will be on the data collected prior to these potential “treatment gaps”.

- If the “treatment gap” is ≤ 8 weeks, then all efficacy data will be summarized together, i.e. data will be analyzed as if the patient had been dosed continuously
- If the “treatment gap” is > 8 weeks, efficacy data collected before and after the treatment gap will be summarized separately.

Data collected under end of study visit (i.e. off-treatment measurement at the end of 12-week or 16-week safety follow up period) will be summarized separately from the data while the patient was on treatment.

For the analysis of Pruritus NRS, the weekly NRS collected during the safety follow-up period, during the treatment gap between amendments 6 and 7, and between amendments 7 and 8 will be separated from the NRS collected during treatment. The primary focus of NRS data will be on the data collected during treatment.

Subgroup analyses for efficacy

Different subgroups within the overall SAF population will be defined as below. The analyses will be performed for the secondary efficacy variables related to EASI, IGA and pruritus NRS by:

- Duration of AD at Day 1 of current study (< 26 years, ≥26 years)
- Baseline body weight of current study ((<70 kg, ≥70-<100 kg, ≥100 kg)
- Baseline BMI of current study (<15, [15-25), [25-30), ≥30)
- Age (≥18-<40, ≥40-<65, ≥65)

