Con meds/procedures	X		X		X		
Efficacy: ^d							
Patient Assessment of Pruritus Intensity via IVRS/IWRS (weekly) ^f	X	weekly throughout the study				X	
IGA, EASI	X						
Safety: ^d							
Weight	X		X		X		
Vital signs	X		X		X		
Ophthalmology exam ^h (select sites and patients)	X		X		X		
Adverse events ^e	X	throughout the study				X	

Study Procedures	Treatment Period						
	Visit (V)	V 31	V 32	V 33	V 34	V 35	V 36
	Week (Wk)	Wk 156	Wk 164	Wk 172	Wk 180	Wk 188	Wk 196
	Day (D)	D 1093	D 1149	D 1205	D 1261	D 1317	D 1373
Visit Window (d)	+/-3d	+/-3d	+/-3d	+/-3d	+/-3d	+/-3d	+/-3d
Laboratory Testing: ^d							
Hematology, Chemistry							
Pregnancy test, WOCBP only ^g	Urine	Urine monthly throughout the study					
HIV Screening							
HBsAg, HBcAb, hepatitis C antibody							
Drug Concentration and Antibody Testing: ^d							
Drug Concentration sample							
ADA sample			X				

- ^a Study drug will be administered weekly, either in the clinic or outside the clinic (self-administration or administration by a care provider).
- ^b If needed, counsel patient on proper dosing diary completion/reporting of each dose of study drug that is administered outside of the clinic.
- ^c Study drug will be dispensed to the patient for each dose that will be administered off-site between the current clinic visit and the next clinic visit. Patients will be instructed to return all study drug at each clinic visit.
- ^d To be collected before the injection of study drug.
- ^e In the event the patient experiences a visible ISR at any clinic visit, the clinical site may photograph the ISR and complete the ISR worksheet.
- ^f Patients will be trained on using the IVRS /IWRS at the baseline visit, and will call into the system weekly to report the overall intensity of their pruritus over the previous week, and to record compliance with self-injection of study drug.
- ^g Patients will be provided with a pregnancy test kit to take home for monthly testing in between clinic visits, or may choose to have the testing done at the study site.
- ^h An acceptable window for performing ophthalmology exams is within +/- 7 days of the visit date. This does not apply to the ophthalmology exam conducted at the baseline visit

Table 13: Schedule of Events – Visits 37 (Week 204) through Visit 43 (Week 252)

Study Procedures	Treatment Period							
	Visit (V)	V 37	V 38	V 39	V 40	V 41	V 42	V 43
	Week (Wk)	Wk 204	Wk 212	Wk 220	Wk 228	Wk 236	Wk 244	Wk 252

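### For treatment gaps over 8 weeks, IGA/EASI values taken at the restart visit before any new injection can enter the post-gap Week-n rows as if they were on-treatment values

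*SAP*

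**What the plan says.** **Gap rules (SAP 5.7).** If the gap is 8 weeks or less, "then all efficacy data will be summarized together, i.e. data will be analyzed as if the patient had been dosed continuously". If it is longer, "efficacy data collected before and after the treatment gap will be summarized separately". The same section reports the end-of-study visit apart from on-treatment data, and separates weekly pruritus NRS collected in follow-up or in either gap. It puts the main efficacy focus on data from before the gaps.

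**Restart visit (SAP 2.3).** For amendment 7, Figure 4 note f says "Patients who have completed their End of Treatment (EOT) visit may resume treatment at visit 31". For amendment 8, Figure 5 notes f and g have patients resume at whichever scheduled visit would have come next.

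**Timing.** In the amendment 8 schedule (SAP 10.2, Table 12) the efficacy block carries the note "To be collected before the injection of study drug". For visits 31 to 43, Protocol 6.2.4 gives "IGA/EASI: visit 31, 37", and SAP Tables 12 and 13 agree.

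**Visit labels (SAP 6.4).** For the countries concerned, every scheduled visit under amendments 7 and 8 except end of study is placed by study day, counted from the first injection in this study.

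**Extent (SAP 2.3).** The first gap occurred "for approximately 113 patients with a median duration of gap around 17 weeks and maximum duration of around 33 weeks". The second affected about 272 patients, with a median of about 10 weeks and a maximum of about 21 weeks.

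**The concern.** A restart-visit IGA/EASI describes a patient who has had no injection for the length of the gap. After a gap of more than 8 weeks it is an off-treatment measurement in the same sense as the end-of-study value, which is taken after 12 or 16 weeks of follow-up and which the SAP reports separately. The pruritus score from the same gap is also set apart. For IGA/EASI there is no equivalent rule, only a before/after split and mapping by study day.

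The proportions with IGA 0 or 1 and with EASI-75 at each visit are key secondary endpoints. A post-gap row with a week label would be read as response on treatment at that week. If it contains pre-dose restart values, it shows partly or mainly how patients fared without drug.

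**Working it through.** The plan has no sample-size or power figure to reproduce: "No formal sample size or power calculations were performed for this study". The check concerns timing and labels, followed by an illustration.

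**1. Is the restart value pre-dose?** Under amendment 7 dosing resumes at visit 31. The amendment 8 schedule and the current protocol have IGA/EASI at visit 31, collected before the injection. If the amendment 7 extension schedule was the same, the value follows the whole gap. That country-specific schedule is not reproduced in the documents, so this step is an inference.

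**2. Where does SAP 6.4 put it?** Nominal end of treatment under amendment 6 is visit 30, day 1037. Study day at restart = 1037 + 7 × gap in weeks.

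| Gap (weeks) | Study day | Window | Row |
|---|---|---|---|
| 9 | 1037 + 63 = 1100 | [1066, 1149] | Week 156 |
| 16 | 1037 + 112 = 1149 | [1066, 1149] | Week 156 |
| 17 (median) | 1037 + 119 = 1156 | [1150, 1261] | Week 172 |
| 33 (maximum) | 1037 + 231 = 1268 | [1262, 1373] | Week 188 |

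The 17-week case lies close to a boundary, so the label may be Week 156 or Week 172. Either way the value sits in an ordinary week row.

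**3. What else is in those rows?** In the amendment 8 schedule, IGA/EASI falls at weeks 156 (visit 31) and 204 (visit 37), which are 204 − 156 = 48 weeks apart, and not at week 172 or 188. Post-gap values in the Week 172 and 188 rows could therefore be largely restart values, alongside any end-of-treatment, early-termination or unscheduled ones. Amendment 7 treatment was to end about 31 December 2017, and visit 37 is not shown to belong to that extension.

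**4. How many patients?** With 2678 enrolled, 113/2678 = 4.2% had the first gap and 272/2678 = 10.2% the second. Some patients may have had both, so the counts should not be added. Both medians exceed 8 weeks, so at most about half of each group (56 of 113; 136 of 272) can fall under the pooling rule. Under amendment 8 only 2 of the 13 visits from 31 to 43 carry IGA/EASI, and the re-entry visit carries none. Both counts are therefore upper bounds.

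**5. How large could the shift be?** If a share s of a row is restart values, with response p on drug and q at restart, the row is low by s × (p − q). The documents give none of the three. With assumed p = 85% and q = 30% to 60%:

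- s = 5%: about 1.2 to 2.8 points
- s = 10%: 2.5 to 5.5 points
- s = 25%: about 6.2 to 13.8 points
- s = 50%: 12.5 to 27.5 points

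These figures only show how the shift depends on s.

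**The case against.** The strongest reply is that the SAP has already dealt with the gaps. Section 5.7 focuses on pre-gap data, keeps long gaps separate, and says openly that all observed values are used, including those after withdrawal from study treatment. Efficacy here is secondary, descriptive and untested. This limits the consequence, and that part stands. It does not settle the classification: the same section sets aside two kinds of off-treatment data and leaves this one out.

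A second reply is that the SAP never calls the restart value post-gap. It is indeed silent. For exposure, Appendix 10.10 runs the gap up to the first new injection, which would place a pre-dose value inside the gap. But 5.7 has no within-gap category for IGA/EASI, and 6.4 gives the value a week label, so by default it lands in a post-gap row.

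A reader might also infer that pooling gaps of 8 weeks or less is wrong. The documents do not support that. SAP 5.5 gives a reason: over such an interruption of weekly dosing, concentrations are not expected to fall far enough to alter the pharmacodynamic effect substantially. The 17-week example lies outside the pooling rule altogether.

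**Conclusion.** The point holds for gaps over 8 weeks. Followed as written, the mapping in SAP 6.4 gives a pre-dose restart IGA/EASI an ordinary week label, and 5.7 does not remove it. Post-gap late-visit rows can mix off-treatment and on-treatment values or consist largely of the former.

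This rests on two conditions: that the amendment 7 extension had IGA/EASI at visit 31 as the amendment 8 table does, and, under amendment 8, that the patient's next scheduled visit carried IGA/EASI.

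A reader might infer that all of the roughly 113 and 272 restarts are affected, or that reported response is too low by some stated amount. Neither follows. The counts are ceilings, and the number of restart values and the response rates are not given. Nor are the main efficacy results in question, since they rest on pre-gap data.

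**What to change.** In SAP 5.7 and 6.4, for gaps over 8 weeks, flag as off-treatment any IGA/EASI dated after the end-of-treatment visit that opened the gap and on or before the date of the first post-gap injection. Treat a same-day value as pre-dose; SAP 6.1 already sets the study baseline for these measures by date alone. Summarise flagged values separately, as is done for end-of-study values and gap-period NRS, and exclude them from the post-gap Week-n rows.

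Gaps of 8 weeks or less can stay pooled under the SAP's stated rationale. Indexing post-gap rows by weeks since restart is optional.

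The cost is one derived flag and a few sentences. Some late post-gap rows lose values and may become sparse, so the number contributing to each should be shown.

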Patients with a missing value at end of treatment visit in the parent study after censoring for rescue treatment use or study withdrawal will be counted as non-responders at the end of treatment visit in the parent study. For patients who had been screened for a phase 3 study (R668-AD-1334 or R668-AD-1416) but could not be randomized because of randomization closure, the patient's status at end of treatment visit in the parent study will be blank. For patients from the 4-week treatment period of phase I or II studies (i.e. R668-AD-0914, R668-AD-1026 and R668-AD-1121), the patient's status at end of treatment visit in the parent study will be blank, since most patients have shown non-response to treatment after a treatment duration of only 4 weeks.

3. The treatment gap between the date of the last dose of dupilumab in the parent study and the first dose date in the current study will be derived and summarized by the following categories: ≤ 8 weeks, > 13 weeks.
4. The following variables for patients' exposure to dupilumab in the parent study will be provided:
 - Cumulative dupilumab dose (mg) in the parent study. For patients who participated in more than one parent study (e.g. patients enrolled in R668-AD-1415 study who previously participated in R668-AD-1334 or R66-AD-1416 study) the cumulative dupilumab dose in parent study is the sum of all dupilumab doses received in all parent studies.
 - Duration of treatment of dupilumab (in weeks) in the parent study, defined as date of last dupilumab injection – date of first study drug injection) + 7]/7. The duration will be categorized by ≤ 4 weeks (ie. 28 days), 5- ≤ 12 weeks, 13- ≤ 16 weeks 17- ≤ 24 weeks, 25- ≤ 52 weeks and > 52 weeks.

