5.6. Treatment Exposure and Observation Period

The duration of treatment exposure period during the study in week is calculated as:

$$[(\text{Date of last study drug injection} - \text{date of first study drug injection}) + 7]/7$$

regardless of unplanned intermittent discontinuations. For the exposure calculation, the two treatment gaps due to patients resuming treatment under protocol amendment 7 or 8 will be excluded. The duration of exposure will be summarized using number of patients, means, SD, minimums, medians, and maximums. A summary of the number of doses will also be provided.

The duration of observation period during the study in weeks is calculated as:

$$[(\text{Date of the last visit} - \text{date of the first study medication dose}) + 1]/7.$$

For the duration of observation period calculation, the study gap for patients who have completed the study under protocol amendment 6 then retry into the study under protocol amendment 7 will be excluded.

The duration of observation periods will be summarized using number of patients, means, SD, minimums, medians, and maximums. The number (%) of patients with observation periods will be presented by specific time periods. The time periods of interest are specified as: ≥ 1 week, ≥ 4 weeks, ≥ 12 weeks, ≥ 16 weeks, ≥ 24 weeks, ≥ 52 weeks, ≥ 76 weeks, ≥ 100 weeks, ≥ 104 weeks, ≥ 124 weeks, ≥ 148 weeks, ≥ 156 weeks, ≥ 164 weeks, ≥ 208 weeks, ≥ 260 weeks, ≥ 272 weeks.

As of protocol amendment 2, the weekly dose of dupilumab was changed from 200 mg to 300 mg. The number of patients exposed to 200 mg dose, the number of 200 mg doses and duration of treatment exposure with 200 mg and 300 mg in weeks will be calculated and summarized separately.

[Appendix 10.10](#) provides the detailed algorithm for calculating duration of treatment exposure and observational period.

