- Gender (Male, Female)
- Race (White, Black or African American, Asian, Others)
- Ethnicity: Hispanic or Latino (yes/no)
- Previous usage of ciclosporin (CsA) (Yes, No)
- Previous usage of methotrexate (MTX) (Yes, No)
- Previous usage of Azathioprine (Aza) (Yes, No)
- Previous use of systemic immunosuppressants for AD (Yes, No)
- History of asthma (Yes, No)
- History of nasal polys (Yes, No)
- History of allergic rhinitis (Yes, No)
- History of food allergies (Yes, No)
- Previous treatment of dupilumab in parent study (Yes, No)
 - For patients who received dupilumab in parent study, data from the following two subgroups will also be summarized.
 - Re-treatment (treatment gap > 8 weeks): – Patients who came from the dupilumab arms of parent studies, and if the gap period between the last dupilumab study drug injection in parent study and the first study drug injection in current study is > 8 weeks (greater than 64 days).
 - Continuous treatment (gap ≤ 8 weeks) – patients who came from the dupilumab arms of parent studies, and if the gap period between the last dupilumab study drug injection in parent study and the first study drug injection in current study is ≤ 8 weeks (less than or equal to 64 days).

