5.10. Analysis of ADA Data

5.10.1. Analysis of ADA Data

The ADA variables described in Section 4.8 will be summarized using descriptive statistics in the ADA analysis set. Frequency tables of the proportion of patients with pre-existing immunoreactivity, treatment-emergent, treatment-boostered, persistent ADA responses, and titer categories will be presented as absolute occurrence (n) and percent of patients (%).

- Pre-existing immunoreactivity is defined as either an ADA positive response in the assay at baseline of parent study with all ADA results negative post first dose of the current study, OR a positive response at baseline of parent study with all ADA results less than 4-fold baseline titer levels of parent study, post first dose of the current study.
- Treatment emergent response is defined as a positive response in the ADA assay post first dose of current study when baseline results of parent study are negative or missing. The treatment emergent responses will be further characterized as Persistent, Indeterminate or Transient
 - Persistent Response – defined as a treatment emergent ADA response with two or more consecutive ADA positive sampling time points separated by greater than (>) 12-week period (greater than 84 days), with no ADA negative samples in between.
 - Indeterminate Response – defined as a treatment-emergent response with only the last collected sample positive in the ADA assay
 - Transient Response - defined as a treatment emergent ADA positive assay response that is not considered persistent or indeterminate.
- Treatment boostered response is defined as a positive response in the ADA assay post first dose that is greater than or equal to 4-fold over baseline titer levels of parent study, when baselines results of parent study are positive.

The baseline used to define ADA status (treatment emergent, pre-existing immunoreactivity, etc) refers to the baseline ADA value in the parent study.

- Titer Values (Titer value category)
 - Low (titer <1,000)
 - Moderate ($1,000 \leq \text{titer} \leq 10,000$)
 - High (titer >10,000)

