10.10. Algorithm to Derive Treatment Exposure and Duration of Observational period

The duration of treatment exposure period during the study in week is calculated as:

$[(\text{Date of last study drug injection} - \text{date of first study drug injection}) + 7]/7$

regardless of unplanned intermittent discontinuations. For the exposure calculation, below two treatment gaps will be excluded.

1. For patients from Germany, France, Poland and Japan who completed the 3-year treatment period under protocol amendment 6 before resuming dupilumab treatment under amendment 7, the duration from the end of treatment under amendment 6 up to the first injection date under amendment 7 will be excluded from the duration of exposure calculation.
2. For patients from Poland, Finland and France who completed the treatment period under protocol amendment 7 before resuming dupilumab treatment under amendment 8, the duration from the end of treatment under amendment 7 up to the first injection date under amendment 8 will be excluded from the duration of exposure calculation.

The following duration of exposure will be summarized using number of patients, means, SD, minimums, medians, and maximums. A summary of the number of doses will also be provided:

- The entire study treatment period
- The treatment period prior to “treatment gap”
- The treatment extension period under protocol amendment 7 for patients from Germany, France, Poland and Japan who completed 3-year treatment
- The treatment extension period under protocol amendment 8 for patients from Poland, Finland and France who completed 3-year treatment and extension period under amendment 7

The duration of observation period during the study in weeks is calculated as:

$[(\text{Date of the last visit} - \text{date of the first study medication dose}) + 1]/7$.

For the duration of observation period calculation, below study gaps will be excluded.

1. For patients from Germany, France, Poland and Japan who completed 3-year study under protocol amendment 6, then reentered the study after consenting to protocol amendment 7, the duration from the end of study under amendment 6 up to date of consent to amendment 7 will be excluded from the duration of observation period calculation.

The following duration of observation periods will be summarized using number of patients, means, SD, minimums, medians, and maximums:

- The entire study period
- The study period prior to protocol amendment 7

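### SAP 5.7 codes an 8-week cut as 64 days, the observation period keeps the amendment 7-to-8 off-study gap, and 10.10 names Germany for Poland (minor)

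*SAP*

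**What the plan says.** **Subgroup cut.** SAP 5.7 splits patients treated with dupilumab in a parent study by the gap between their last parent-study injection and their first injection here. Re-treatment applies if the gap to "the first study drug injection in current study is > 8 weeks (greater than 64 days"). Continuous treatment applies if the gap to "the first study drug injection in current study is ≤ 8 weeks (less than or equal to 64 days"). Elsewhere the SAP converts weeks at 7 days: "The duration will be categorized by ≤ 4 weeks (ie. 28 days") in 4.2, and "separated by greater than (>) 12-week period (greater than 84 days") in 5.10.1.

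**Observation period.** For exposure, SAP 5.6 states that "the two treatment gaps due to patients resuming treatment under protocol amendment 7 or 8 will be excluded". For the observation period, the same section removes only one interval: "study gap for patients who have completed the study under protocol amendment 6 then retry into the study under protocol amendment 7 will be excluded". Appendix 10.10 opens in the plural, "For the duration of observation period calculation, below study gaps will be excluded", but lists a single item: "the duration from the end of study under amendment 6 up to date of consent to amendment 7 will be excluded".

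**Countries.** The amendment 8 observation summary in 10.10 is for Germany, Finland and France. The matching exposure summary in the same appendix is for Poland, Finland and France.

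**The concern.** These are definitions that a programmer will code as written.

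- The 64-day figure puts patients with a gap just over 8 weeks into the group labelled as 8 weeks or less. SAP 4.2 (item 3) tabulates the same parent-study interval with an 8-week category and no day count. Two tables carrying the same label could therefore disagree.
- Leaving the second off-study interval in the observation period overstates follow-up for patients who re-entered after an amendment 7 end-of-study visit. Long-term safety is the primary objective, so duration of follow-up is basic context for the report.
- Followed literally, the amendment 8 observation summary selects a country with no amendment 8 extension (Table 2 lists none for Germany). It omits Poland, which was extended to 5 years.

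**Working it through.** **1. The 64-day figure.** The inputs are the SAP's own conversions:
- 28/4 = 7 days per week (4.2).
- 84/12 = 7 (5.10.1).
- Week 8 has target study day 57 in 6.4, and (57 − 1)/7 = 8.

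On that basis 8 × 7 = 56, so the plan's 64 is not reproduced. Variants tried: 56 + 1 = 57; 56 + 3 (visit window) = 59; 56 + 7 = 63; 9 weeks = 63. Only 56 + 7 + 1 gives 64, and no such rule is stated. 64/7 = 9.14 weeks. The misplaced band is days 57 to 64, which is 8 days wide. The number of patients in it is not given.

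**2. The two off-study intervals side by side.**

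| SAP text | Amendment 6 to 7 | Amendment 7 to 8 |
|---|---|---|
| 1.2.4 change table, observation calculation | accounted for | accounted for |
| 4.6.1, overall study period = treatment + follow-up | outside | outside |
| 4.6.1, AE with onset in the interval | not a TEAE | not a TEAE |
| 5.6 and 10.10, exposure | removed | removed |
| 5.6 and 10.10, observation period | removed | not mentioned |

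Only the last cell breaks the pattern.

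**Illustrative size.** Inputs from SAP 2.3 and 2.2: about 272 patients with the second treatment gap, median about 10 weeks, maximum about 21 weeks; 12-week follow-up; 2,678 enrolled. Assumption: end of study exactly 12 weeks after the gap starts.
- The median of 10 is below 12, so at most about 272/2 = 136 patients have any off-study time.
- Off-study time per patient is at most 21 − 12 = 9 weeks.
- 136 × 9 = 1,224 patient-weeks; 1,224 × 7/365.25 = 23.5 patient-years.
- Averaged over all enrolled: 136 × 63/2,678 = 3.2 days.

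The assumption matters. The amendment 8 schedule (SAP Table 14) allows ±30 days at end of study. The amendment 7 schedules for Poland and France are not in the documents. If visits 30 days early were possible, end of study could fall 84 − 30 = 54 days after the gap starts. The upper half could then have 147 − 54 = 93 days each and the lower half 70 − 54 = 16 days each. That gives 136 × 93 + 136 × 16 = 14,824 days, or about 41 patient-years.

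**Which minimum-duration rows.** Observation weeks = (last visit − first dose + 1)/7. With a last visit on 01-Dec-2018 and 63 off-study days, a patient is wrongly counted:
- in ≥208 weeks if first dosed 06-Oct to 07-Dec-2014;
- in ≥164 weeks if first dosed 10-Aug to 11-Oct-2015;
- in ≥124 weeks if first dosed 16-May to 17-Jul-2016.

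In Poland and France, amendment 7 treatment ended about 31 December 2017 whatever the entry date (SAP 2.3), and enrolment finished by the end of May 2017 (SAP 2.2). Several rows are therefore exposed.

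**3. Country lists for the amendment 8 gap or extension.**
- Poland, Finland and France: SAP 2.3 (text and Table 2), 4.6.1, 5.5, and the 10.10 exposure text.
- Germany, Finland and France: the 10.10 observation summary.
- Germany, France, Poland and Japan, for up to two gaps: 5.7, which omits Finland.
- Poland only: 6.4.

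**The case against.** The best defence is that all three are clerical and the intent can be recovered. The 64-day rule is used in both definitions, so each patient still falls in exactly one group and only one descriptive subgroup split moves. The change table in 1.2.4 and the study-period definition in 4.6.1 already show that both off-study gaps were meant to be handled. The correct country list stands in the parallel exposure bullet. This stands as an argument about severity. It does not make the text right. Nor can observation be read as plain calendar time, because the amendment 6-to-7 interval is removed from it.

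Three stronger readings are tempting and are not supported.

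- *The primary TEAE rates are biased.* Appendix 10.5 divides by exposure in the TEAE period and does not name the observation period as the denominator. Rates would move only if programming reused the observation period as person-time.
- *One row, such as ≥208 weeks, carries most of the error.* The row dates above show otherwise, and no enrolment dates by country are given. The 01-Dec-2018 cut-off also does not cover France (SAP 7 and 10.8).
- *23.5 patient-years is a ceiling.* It holds only under the 12-week assumption. End of study is timed from the last dose, while the gap is counted from the end-of-treatment date.

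The 64-day figure also does not reach the amendment gaps. The 8-week rules for those in 5.5, 5.7 and 5.11.2 carry no day count.

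**Conclusion.** All three slips are in the SAP text and should be corrected; severity is minor. Gaps of 57 to 64 days are classed against their label. Off-study time after an amendment 7 end-of-study visit is counted as observation. The amendment 8 observation summary leaves out Poland as written.

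The affected outputs are all descriptive: one efficacy subgroup split, the observation-duration summaries and several minimum-duration rows. How many patients are affected cannot be determined from the documents. The figure of at most about 136 patients, at most about 9 weeks each (23.5 patient-years), is an illustration under an assumed 12-week end-of-study visit. The true figure under that assumption is probably well below it, because few patients would reach the maximum gap; early visits could push it higher.

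The 56-day reading rests on the label being the intent. SAP 5.5 gives a pharmacological reason for an 8-week limit, for the amendment gaps, and nothing in the documents gives one for 64 days.

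**What to change.** 1. In SAP 5.7, change 64 to 56 days in both subgroup definitions.
2. In SAP 5.6 and 10.10, add the amendment 7-to-8 study gap to the observation-period exclusions, worded like the existing rule: from end of study under amendment 7 up to consent to amendment 8. Both rules would then still end at consent, while the interval that 4.6.1 keeps out of TEAEs runs to the first injection. The SAP should say whether that difference is intended.
3. In the 10.10 observation summary for amendment 8, change the countries to Poland, Finland and France. Reconcile the second-gap lists in 5.7 (Finland missing) and 6.4 (Poland only).

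The cost is a few SAP lines and minor programming, with no new data. SAP 7 already foresees an addendum for later analyses, and protocol section 9 allows SAP revision before database lock.
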